4.10. Analyses on Japan Subpopulation

A set of key study population, efficacy, safety, immunogenicity, PD and PK analyses will be repeated in the Japan subpopulations (as defined in Section 3, Analysis Sets). Details are provided in the OPS.

4.11. Interim Analyses

There will be one unblinded interim analysis for futility. Periodic review of safety data by an independent data monitoring committee (IDMC) will also be performed. Other than the emergency unblinding procedures described in the protocol, all personnel having direct responsibility for the conduct of the study will remain blinded to treatment groups for all data until the database is frozen.

4.11.1. IDMC Safety Review

IDMC will periodically review unblinded safety data from the three Phase III studies in the severe asthma program: 206713, 213744 (this study) and 206785, in accordance with the IDMC Charter. IDMC will also review safety data from study 212895, an open-label extension study including participants who were previously enrolled in study 206713 or 213744 when sufficient data is collected.

The IDMC will review all safety data, including AEs and serious adverse events (SAEs) and adverse events of special interest (AESI), laboratory parameters, including

haematological and clinical chemistry parameters and ECG assessments from the three studies for identification of any potential safety signals. The safety data analyses for the IDMC reviews will be performed by an independent Statistical Data Analysis Centre (SDAC).

4.11.2. Unblinded Interim Analysis for Futility

An unblinded interim analysis for futility will be conducted by an independent SDAC in conjunction with an IDMC to maintain study integrity.

The futility analysis will evaluate efficacy based on the primary endpoint of annualised rate of clinically significant exacerbations using interim data from Phase III studies 206713 and 213744 (this study) when approximately 675 participants are randomised across both studies. The stopping rule is binding, i.e. if the stopping criteria is met then the recommendation will be to stop, conditional on the IDMC deeming that there is no delayed onset of clinical efficacy. Should it be judged that there is delayed onset then this may invalidate an assumption of the interim analysis that the pre-interim data is reflective of post-interim data which could result in inflation of type 2 error. In such a situation, the IDMC will use their expert judgment in determining their recommendation.

Recruitment into the study will continue whilst the futility analysis is taking place. Any communication to the sites regarding the decision will only take place if a decision to stop the study is made. Should the studies be stopped, all on-going participants will complete their follow-up period but will not receive any further doses whilst no further participants will be recruited into the study.

The full details of the process are included in IDMC Charter.

4.11.2.1. Decision Rule

The interim analysis will be based on the predictive probability of meeting the end of study (program) success criteria (defined as statistical significance at a two-sided 5% alpha level in **both** studies 206713 and 213744). Should the predictive probability of success be less than or equal to 0.25 then the studies will be stopped for futility.

The futility rule:

Futility	Continue
Predictive probability (statistical	Predictive probability (statistical
significance two-sided 5%) in both	significance two-sided 5%) in both 206713
$206713 \& 213744) \le 0.25$	& 213744) > 0.25

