2. STATISTICAL HYPOTHESES

The primary study objective is to test for the superiority of GSK3511294 100 mg SC + SoC following two doses (at Week 0 and at Week 26) compared with placebo + SoC, assessed by the annualised rate of clinically significant exacerbations measured over the study intervention period of 52 weeks.

The study will test at a 5% two-sided significance level the null hypothesis that there is no difference in annualised exacerbation rate between GSK3511294 and placebo.

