4.11.2.2. Methodology

Predictive probability of success will be used to determine the decision of futility or continue. The methodology involves predicting the remainder of the data on the primary endpoint for participants that have not yet completed or yet to be randomised into the study. The primary analysis is then performed separately for each study on this "complete" dataset, i.e. comprising of observed pre-interim data and predicted post-interim data. The success criteria is applied at this stage. To account for uncertainty attached to parameters at the interim, and therefore uncertainty in the predicted remaining

data (due to the limited data), this step is performed 1000s of times. The proportion of iterations that meet the success criteria (statistical significance in both studies) gives the predictive probability of success. If this is low (≤ 0.25), the studies will stop for futility Specific steps on the methodology are given below.

- 1. Data on the primary endpoint (number of clinically significant exacerbations) will be pooled across the two pivotal studies (206713, 213744) for the purposes of predicting post-interim data. Pooling allows for a more precise estimate of the overall treatment effect resulting in improved operating characteristics. Since these are replicate studies the pooling is deemed appropriate. Participants with at least one month of time in the study since randomisation will be included in the interim analysis (the negative binomial model accounts for varying follow-up time across participants).
- 2. The primary analysis with pooled data across both studies will be fitted (plus an additional fixed term for study) in a Bayesian framework (non-informative priors on all model parameters). Posterior distributions for the β model parameters and k dispersion parameter will be obtained with 1000s of sets of samples (iterations) taken from these posterior distributions which will be shown in the steps below to be used to predict exacerbations in the post-interim period.
- 3. For each iteration the expected number of exacerbations pre and post-interim is calculated as $\hat{y}_{i,1}$ and $\hat{y}_{i,2}$, respectively, for each participant, i. The predictions for post-interim data will be based on the interim posterior distribution. To calculate $\hat{y}_{i,1}$ and $\hat{y}_{i,2}$, the steps are as follows:

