 - 1. The design matrix (Z) is multiplied with the set of posterior β samples and then back-transformed (exponentiated) to give expected annualised

exacerbation rate for each participant (μ_i) based on the interim data. Note: for participants yet to be randomised, and therefore without values observed for baseline covariates, bootstrapping from already randomised participants will be performed.

- 2. The expected exacerbation rate for the pre-interim and post-interim periods are calculated by multiplying μ_i by the pre-interim and post-interim times in the study for the participant: $\hat{y}_{i,1} = \mu_i \times t_{i,1}$ and $\hat{y}_{i,2} = \mu_i \times t_{i,2}$.
- 3. For the two periods (pre and post-interim), the number of exacerbations within each period is negative binomial. The distribution of one period conditional upon the other, within a participant, is also negative binomial [Keene, 2014]. The negative binomial parameters for the post-interim period are calculated for each participant and set of posteriors samples (iteration):

$$p_{i,2} = \frac{\frac{1}{k} + \hat{y}_{i,1}}{\frac{1}{k} + \hat{y}_{i,1} + \hat{y}_{i,2}}$$
$$k_{i,2} = k_1 + count_{i,1}$$

Where k_1 is the sampled dispersion parameter, $count_{i,1}$ is the number of exacerbations for participant *i* in period 1 (pre-interim), *i* is the participant and j=1,2 is the period (pre, post-interim).

Using these parameters, simulate a participant's number of clinically significant exacerbations for post-interim data for each set of posterior samples

- 4. The pre-interim observed data (one set) will be combined with each set of postinterim data (1000s of sets) to create 1000s of end of study datasets
 - 1. Each participant's exacerbation count will be the summation of pre-interim observed count (if the participant was randomised at least one month before the interim data cut) plus the post-interim simulated exacerbation count (if the participant did not complete before the interim).
 - 2. Each participant's length of time in the study will now be the assumed average length of time in the study, which is set at 0.86 years.
- 5. The primary analysis model is applied to each iteration (dataset), each study separately. The p-value for the treatment effect (rate ratio) will be calculated. For each iteration, if the success criteria (statistical significance at 5% two-sided level for both studies) is met then the iteration is marked as success (flag as 1), or if not then fail (flag as 0).

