5.1.1. Primary Endpoint

The assumed true annualised rate of exacerbations in the placebo arm is 1.18. Based on an assumed true treatment difference of a 50% reduction in annualised exacerbation rate between GSK3511294 + SoC and placebo + SoC, a sample size of 375 randomised participants (250 to GSK3511294, 125 to placebo) will provide 99% power for the primary endpoint at a 5% two-sided significance level [PASS, 2020].

The assumptions for the placebo rate and treatment effect are median values from an elicitation exercise which used Phase 3 anti-IL-5/5R historical data (~50% reduction in exacerbations) and expert opinion. The sample size is based also on an assumption of 0.8 for the dispersion parameter which was observed in two mepolizumab studies [Pavord, 2012; Ortega, 2014]. It was assumed that 14% of participant-years data will be missing due to study withdrawal, which is also consistent with mepolizumab studies.

Based on the assumptions above, the minimum observed treatment difference estimated to result in significance at the 5% two-sided significance level is a 27% reduction in exacerbations for GSK3511294 + SoC compared with placebo + SoC (rate ratio of 0.73).

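### The futility rule's definition of success states no direction, so read literally it returns Continue when depemokimab is clearly worse than placebo in both studies

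*SAP*

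**What the plan says.** The rule is in SAP 4.11.2. Success at the end of the programme is "defined as statistical significance at a two-sided 5% alpha level in" both pivotal studies, and the threshold follows: "Should the predictive probability of success be less than or equal to 0.25 then the studies will be stopped for futility". The two-column rule table in 4.11.2.1 repeats the two-sided 5% criterion.

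Section 4.11.2.2 uses the same definition: "The proportion of iterations that meet the success criteria (statistical significance in both studies) gives the predictive probability of success". In step 5 the p-value for the treatment effect is calculated in each simulated end-of-study dataset, and "if the success criteria (statistical significance at 5% two-sided level for both studies) is met then the iteration is marked as success". The success column of Table 5 (4.11.2.3) is also headed by significance in both studies. None of these places mentions the sign of the effect.

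Direction appears only outside the rule. The objective in SAP section 2 is to "test for the superiority of GSK3511294 100 mg SC + SoC" against placebo, although the null hypothesis in the same section is that "there is no difference in annualised exacerbation rate between GSK3511294 and placebo", tested two-sided. SAP 5.1.1 gives the smallest significant effect as a 27% reduction (rate ratio 0.73). Section 4.11.2.3 gives one expected interim trigger for futility, an observed rate ratio of about 0.70.

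**The concern.** A two-sided p-value below 5% can arise from benefit or from harm. If the success flag depends on that p-value alone, iterations in which active is significantly worse in both studies are scored 1 and raise the predictive probability of success. A clearly harmful interim result would then push the probability above 0.25 and return Continue.

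The operating characteristics cannot reveal this. Table 5 covers true rate ratios from 0.5 to 1 only, so the harm side was not tabulated, and over that range a directional and a non-directional flag give almost the same figures. What is at stake is the output of a pre-specified rule that an independent SDAC will run for two studies while recruitment continues.

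**Working it through.** **Inputs, all from the SAP.** Placebo rate 1.18 per year, dispersion k = 0.8, 250 active and 125 placebo (5.1.1); mean time in study 0.86 years (4.11.2.2, step 4); information fraction f = 0.60 (4.11.2.3); stop if the predictive probability is 0.25 or less (4.11.2.1).

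**Step 1: reproduce the plan's power.** For a rate ratio RR, the variance of the log rate ratio at the end of one study is

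V(RR) = [1/(1.18 × RR × 0.86) + 0.8]/250 + [1/(1.18 × 0.86) + 0.8]/125.

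At RR = 0.5 this is 2.7708/250 + 1.7854/125 = 0.01108 + 0.01428 = 0.02537, so the standard error is 0.1593. Power = Φ(0.6931/0.1593 − 1.96) = Φ(2.39) = 99.2%, against the stated 99%. The smallest significant rate ratio is exp(−1.96 × 0.1593) = 0.732, against the stated 0.73. The inputs are therefore read correctly.

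**Step 2: approximate the futility procedure.** In each study the interim log rate ratio has variance V/f. The two interim estimates are averaged to give a posterior for a common effect with variance V/(2f) (flat prior). Each study's final estimate is f × (its interim estimate) + (1 − f) × (the predicted remainder), where the remainder has mean equal to the posterior draw. Given that draw, the final estimate has variance (1 − f)V. Success means both final tests are significant. The procedure was run with 40,000 simulated pairs of studies per true rate ratio, once with the flag as printed and once with RR < 1 required.

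| True RR | P(stop), SAP Table 5 | P(stop), as printed | P(stop), RR < 1 required |
|---|---|---|---|
| 0.5 | 0.01 | 0.01 | 0.01 |
| 0.6 | 0.11 | 0.10 | 0.10 |
| 0.7 | 0.42 | 0.38 | 0.38 |
| 0.8 | 0.76 | 0.73 | 0.73 |
| 0.9 | 0.94 | 0.92 to 0.93 | 0.93 |
| 1.0 | 0.98 | 0.97 to 0.98 | 0.99 |
| 1.25 | not given | 0.71 | 1.00 |
| 1.3 | not given | 0.60 | 1.00 |
| 1.5 | not given | 0.20 | 1.00 |
| 1.75 | not given | 0.02 | 1.00 |
| 2.0 | not given | 0.001 | 1.00 |

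The approximation agrees with Table 5 to within about 0.04. At RR = 1 the stated 0.98 lies between the two versions, so Table 5 does not show which one was programmed.

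**Step 3: find where the printed rule turns back to Continue.** Suppose both studies show an interim rate ratio of 1.31, so the log rate ratio is 0.2700.

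- V(1.31) = 0.02049, standard error 0.1432; significance on the harm side needs a final log rate ratio above 1.96 × 0.1432 = 0.2806.
- Each final estimate has predictive mean 0.2700 and variance 0.4² × 0.02049/1.2 + 0.4 × 0.02049 = 0.00273 + 0.00820 = 0.01093, standard deviation 0.1045.
- The chance of significant harm in one study is 1 − Φ((0.2806 − 0.2700)/0.1045) = 1 − Φ(0.10) = 0.46.
- The shared posterior draw gives the two studies a correlation of 0.00273/0.01093 = 0.25, and the bivariate normal probability that both are significant is 0.25.

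This is the threshold. Below about 1.31 the rule says stop; above it, Continue. For information fractions of 0.5 to 0.8 the crossing point lies between 1.30 and 1.32. The predictive probability as printed is 0.22 at an observed 1.30, 0.37 at 1.35 and 0.80 at 1.50. With direction required it is zero to four decimals at all three.

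**Limits.** This is a normal approximation with equal information in the two studies. It puts the benefit-side trigger at an observed rate ratio of about 0.75, where the SAP expects about 0.70 (possibly an average over futility cases). The harm-side figures should be read as approximate.

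**The case against.** The strongest reply is that direction is supplied by context. The objective is superiority, the significance boundary is quoted only as a reduction, and one interim trigger is given, on the benefit side. The program and the IDMC charter, which is said to hold the full process, are not in the documents. This stands as far as intent goes. A reader might infer that the SDAC coded the rule without direction, and nothing in the documents supports that. It does not repair the text, because step 5 is an instruction to a programmer and, followed literally, it omits the condition.

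The second reply is that the IDMC would not be misled. It stands in large part. A reader might infer that the rule would compel the studies to go on in the face of harm, but SAP 4.11.2 makes the rule binding only towards stopping, and nothing obliges the IDMC to continue. The interim outputs in 4.11.2.4 include the adjusted rate ratio by time period and the primary analysis table for each study, so a ratio above 1.3 in both would be visible. The periodic safety review is a weaker backstop for this outcome: protocol 8.2.2 and 8.4 keep exacerbations out of the adverse event data unless they are serious, and 8.4.7 does not list them as events of special interest.

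A reader might also infer that the rule stops less readily the worse the drug looks. That is true only above a rate ratio of 1. From 0.5 to 1 the probability of stopping rises from 0.01 to 0.98 in Table 5, as it should.

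Finally, clear harm is improbable on the plan's own assumption of about a 50% reduction. That bears on severity and leaves the wording as it is.

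**Conclusion.** The point holds as a gap in the specification. As printed, the success criterion has no direction, and a literal reading returns Continue at an observed interim rate ratio above about 1.31 in both studies. The probability of stopping falls from about 0.97 at a true rate ratio of 1 to about 0.60 at 1.3 and 0.20 at 1.5, where a directional rule would stop almost always. These sizes rest on the SAP's planning inputs, 60% information and the approximation described above.

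The documents suggest that benefit was intended, and they do not show how the rule was coded. The final test, its type I error and the sample size are untouched. Severity is minor, and the correction is worth making because the rule's printed output is wrong in one region and the repair has no drawback.

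**What to change.** In SAP 4.11.2.1 (text and rule table), in the definition of success in 4.11.2.2, and in step 5, define success as a rate ratio (GSK3511294/placebo) below 1 and two-sided p < 0.05 in both studies, and flag an iteration only when both conditions hold in both studies. Confirm that the SDAC program and the IDMC charter use the same definition. Add at least one row with a true rate ratio above 1 to Table 5.

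The cost is one phrase in each place, one condition in the program if it is not already there, and one further simulation scenario. Existing Table 5 entries for rate ratios 0.5 to 0.9 are essentially unchanged. If the program had no direction, the probability of futility at a rate ratio of 1 would rise by about 0.01.

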4.11.2.2. Methodology

Predictive probability of success will be used to determine the decision of futility or continue. The methodology involves predicting the remainder of the data on the primary endpoint for participants that have not yet completed or yet to be randomised into the study. The primary analysis is then performed separately for each study on this "complete" dataset, i.e. comprising of observed pre-interim data and predicted post-interim data. The success criteria is applied at this stage. To account for uncertainty attached to parameters at the interim, and therefore uncertainty in the predicted remaining

data (due to the limited data), this step is performed 1000s of times. The proportion of iterations that meet the success criteria (statistical significance in both studies) gives the predictive probability of success. If this is low (≤ 0.25), the studies will stop for futility Specific steps on the methodology are given below.

- 1. Data on the primary endpoint (number of clinically significant exacerbations) will be pooled across the two pivotal studies (206713, 213744) for the purposes of predicting post-interim data. Pooling allows for a more precise estimate of the overall treatment effect resulting in improved operating characteristics. Since these are replicate studies the pooling is deemed appropriate. Participants with at least one month of time in the study since randomisation will be included in the interim analysis (the negative binomial model accounts for varying follow-up time across participants).
- 2. The primary analysis with pooled data across both studies will be fitted (plus an additional fixed term for study) in a Bayesian framework (non-informative priors on all model parameters). Posterior distributions for the β model parameters and k dispersion parameter will be obtained with 1000s of sets of samples (iterations) taken from these posterior distributions which will be shown in the steps below to be used to predict exacerbations in the post-interim period.
- 3. For each iteration the expected number of exacerbations pre and post-interim is calculated as $\hat{y}_{i,1}$ and $\hat{y}_{i,2}$, respectively, for each participant, i. The predictions for post-interim data will be based on the interim posterior distribution. To calculate $\hat{y}_{i,1}$ and $\hat{y}_{i,2}$, the steps are as follows:
 - 1. The design matrix (Z) is multiplied with the set of posterior β samples and then back-transformed (exponentiated) to give expected annualised

exacerbation rate for each participant (μ_i) based on the interim data. Note: for participants yet to be randomised, and therefore without values observed for baseline covariates, bootstrapping from already randomised participants will be performed.

- 2. The expected exacerbation rate for the pre-interim and post-interim periods are calculated by multiplying μ_i by the pre-interim and post-interim times in the study for the participant: $\hat{y}_{i,1} = \mu_i \times t_{i,1}$ and $\hat{y}_{i,2} = \mu_i \times t_{i,2}$.
- 3. For the two periods (pre and post-interim), the number of exacerbations within each period is negative binomial. The distribution of one period conditional upon the other, within a participant, is also negative binomial [Keene, 2014]. The negative binomial parameters for the post-interim period are calculated for each participant and set of posteriors samples (iteration):

$$p_{i,2} = \frac{\frac{1}{k} + \hat{y}_{i,1}}{\frac{1}{k} + \hat{y}_{i,1} + \hat{y}_{i,2}}$$
$$k_{i,2} = k_1 + count_{i,1}$$

Where k_1 is the sampled dispersion parameter, $count_{i,1}$ is the number of exacerbations for participant *i* in period 1 (pre-interim), *i* is the participant and j=1,2 is the period (pre, post-interim).

Using these parameters, simulate a participant's number of clinically significant exacerbations for post-interim data for each set of posterior samples

- 4. The pre-interim observed data (one set) will be combined with each set of postinterim data (1000s of sets) to create 1000s of end of study datasets
 - 1. Each participant's exacerbation count will be the summation of pre-interim observed count (if the participant was randomised at least one month before the interim data cut) plus the post-interim simulated exacerbation count (if the participant did not complete before the interim).
 - 2. Each participant's length of time in the study will now be the assumed average length of time in the study, which is set at 0.86 years.
- 5. The primary analysis model is applied to each iteration (dataset), each study separately. The p-value for the treatment effect (rate ratio) will be calculated. For each iteration, if the success criteria (statistical significance at 5% two-sided level for both studies) is met then the iteration is marked as success (flag as 1), or if not then fail (flag as 0).
- 6. The mean of these success flags in step 7 is calculated to give the predictive probability of success.
- 7. If the predictive probability of success is ≤ 0.25 then the futility criteria has been met.

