4.11.2.3. Timing and Operating Characteristics

The proposed timing of the futility analysis is when approximately 675 participants have been randomised across the studies. At this time it is estimated that approximately 200 participants will have completed the studies and 500 received both doses (i.e. at least 6 months worth of data). The median follow-up time in the interim analysis is estimated to be 9 months with the information fraction for the primary endpoint estimated to be 60%, where information fraction is calculated as:

$$Information \ fraction = \frac{\sum_{i=1}^{n(interim)} length \ of \ time \ in \ study \ at \ interim_i}{\sum_{i=1}^{750} length \ of \ time \ expected \ in \ complete \ study_i}$$

Table 5 shows operating characteristics of the futility analysis for a range assumed true treatment effects when approximately 725 participants have been randomised (proposed interim timing). Operating characteristics were obtained by simulating 5,000 studies and following the steps in Section 4.11.2.2 for each simulated study. Operating characteristics are obtained from the aggregate of these simulations.

As this is a futility analysis and there is no opportunity to stop for efficacy the type 1 error (calculated under the null hypothesis of assumed rate ratio = 1) is controlled well below the 5% level. The power of each study is approximately 99%, compared with >99% in the scenario where there is no futility analysis (as described in the protocol). The

expected observed rate ratio at the interim to trigger futility is expected to be approximately 0.70.

Assumed treatment effect (rate ratio depemokimab vs. placebo)	Probability of success (statistical significance in both studies)	Power ¹ : 206713	Power1: 213744	Probability of futility
1	<0.01	<0.01	<0.01	0.98
0.9	0.01	0.04	0.02	0.94
0.8	0.08	0.18	0.13	0.76
0.7	0.37	0.50	0.44	0.42
0.6	0.78	0.85	0.82	0.11
0.5	0.98	0.98	0.98	0.01

Table 5 Operating Characteristics of Futility Analysis

¹ at two-sided 5% significance level for end of study test and incorporating the possibility of futility

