4.11.2.5. Decision Making

The outputs from the interim analysis will be forwarded from the SDAC to the IDMC. As the stopping rule is binding, the decision will be communicated from the SDAC to the IDMC and then to GSK following agreement from the IDMC.

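### The futility algorithm (SAP 4.11.2.2, step 3.3) prints the wrong negative binomial size: dispersion plus count, where 1/dispersion plus count is needed

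*SAP*

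**What the plan says.** SAP 4.11.2.2 fits the pooled primary model in a Bayesian framework. Step 2 names the parameters: "Posterior distributions for the β model parameters and k dispersion parameter will be obtained". Step 3.3 then takes each participant's post-interim count, given the pre-interim count, as negative binomial with two parameters:

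- a probability, p = (1/k + ŷ1)/(1/k + ŷ1 + ŷ2), where ŷ1 and ŷ2 are the expected pre- and post-interim counts;
- a size, "k_{i,2} = k_1 + count_{i,1", where k_1 "is the sampled dispersion parameter".

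SAP 5.1.1 gives the planning value: "The sample size is based also on an assumption of 0.8 for the dispersion parameter".

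On the operating characteristics in Table 5, SAP 4.11.2.3 states: "Operating characteristics were obtained by simulating 5,000 studies and following the steps in Section 4.11.2.2 for each simulated study".

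Both studies stop if the predictive probability of significance in both is 0.25 or less (SAP 4.11.2.1). SAP 4.11.2 calls the rule binding and says that if it is met "then the recommendation will be to stop, conditional on the IDMC deeming that there is no delayed onset of clinical efficacy". Under SAP 4.11.2.5, "the decision will be communicated from the SDAC to the IDMC and then to GSK following agreement from the IDMC".

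**The concern.** The two parameters of one distribution are printed on different scales. The probability uses the reciprocal of the dispersion; the size uses the dispersion itself, under the same name that step 2 gives to k. They describe the intended distribution only at k = 1.

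This line generates the data behind the stopping decision for both pivotal studies. If it is coded as printed and the sampled k is below 1, the simulated final datasets hold too few events, predictive probability is biased down, and the 0.25 threshold is met more often than Table 5 states. Above k = 1 the bias goes the other way.

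**Working it through.** **1. Which scale is 0.8 on?** Inputs from SAP 5.1.1: placebo rate 1.18, 250 vs 125 participants, 14% of participant-years missing (mean exposure 0.86 years), two-sided 5%. With variance mu + k·mu²:

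Var(log RR) = (1/(0.86·1.18) + k)/125 + (1/(0.86·1.18·RR) + k)/250

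At k = 0.8 and RR 0.5: (0.985 + 0.8)/125 + (1.971 + 0.8)/250 = 0.02537, so SE = 0.1593. Then |ln 0.5|/SE = 4.352 and power = Φ(4.352 − 1.960) = 99.2% (stated 99%). The minimum significant rate ratio is exp(−1.960 × 0.1593) = 0.732 (stated 0.73). All 12 cells of Table 7 are reproduced within 0.5 point.

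If 0.8 were the gamma shape (k = 1/0.8 = 1.25), power at placebo rate 1.18 would be 56/85/98% for reductions of 30/40/50%, against the stated 65/91/99%, and the minimum significant rate ratio would be 0.709. So 0.8 is the variance-scale dispersion and the matching size is 1/0.8 = 1.25.

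**2. The conditional distribution.** Under the gamma-Poisson model, the post-interim count given pre-interim count c is negative binomial with size 1/k + c and exactly the printed p. The conditional means are:

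- correct: (1/k + c)·ŷ2/(1/k + ŷ1)
- as printed: (k + c)·ŷ2/(1/k + ŷ1)

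Check with 4 million simulated pairs, k = 0.8, ŷ1 = 0.59, ŷ2 = 0.40:

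| Pre-interim count | Simulated mean | Size 1/k + c | Size k + c |
|---|---|---|---|
| 0 | 0.272 | 0.272 | 0.174 |
| 1 | 0.489 | 0.489 | 0.391 |
| 2 | 0.706 | 0.707 | 0.609 |
| 3 | 0.920 | 0.924 | 0.826 |

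**3. Share of post-interim events lost.** Averaged over counts, this is 1 − (k + ŷ1)/(1/k + ŷ1). At k = 0.8:

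- not yet randomised (ŷ1 = 0): 1 − 0.8/1.25 = 36%
- placebo at 6 months (ŷ1 = 0.59): 1 − 1.39/1.84 = 24%
- active at 6 months, RR 0.5 (ŷ1 = 0.295): 1 − 1.095/1.545 = 29%

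Pooled over follow-up profiles built from the SAP's interim figures (200 completed, 500 with both doses), the loss is 23% to 32%, depending on how remaining time and uncertainty in k are handled. It depends strongly on k: 63–69% at k = 0.5, none at k = 1, and 36–44% too many events at k = 1.2.

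**4. Effect on the futility rule.** Simulation: two studies of 375 (2:1), placebo rate 1.18, k = 0.8, mean time 0.86 years, interim at 675 randomised, pooled negative binomial fit, 300 approximate posterior draws, both size forms applied to the same 1,000 trials. SE of each probability is at most 0.016.

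| True RR | P(futility), 1/k form | P(futility), as printed | Table 5 |
|---|---|---|---|
| 0.9 | 0.944 | 0.962 | 0.94 |
| 0.8 | 0.781 | 0.847 | 0.76 |
| 0.7 | 0.437 | 0.523 | 0.42 |
| 0.6 | 0.129 | 0.182 | 0.11 |
| 0.5 | 0.014 | 0.029 | 0.01 |

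Paired differences (SE) are +8.6 points (0.9) at RR 0.7, +5.3 (0.8) at RR 0.6 and +1.5 (0.4) at RR 0.5. Success in both studies falls from 0.351 to 0.322, 0.769 to 0.733, and 0.972 to 0.960 respectively. A coarser simulation with a different follow-up profile (400 trials per scenario) gives 0.42 vs 0.49, 0.12 vs 0.18 and 0.01 vs 0.02.

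The SAP sets the interim at 675 randomised but describes Table 5 as "when approximately 725 participants have been randomised (proposed interim timing". At 725 the differences are +8.4, +6.0 and +0.7 points. The largest gap from Table 5 is then 5 points for the 1/k form and 13 for the printed form, against 2 and 10 at 675.

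At RR 0.7 and 675 randomised, the difference is +27.5 points if k = 0.5 and −5.5 if k = 1.2.

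**The case against.** The strongest reply is that this is notation only. The left-hand side is a size parameter, the p line uses an unsubscripted k, and k_1 could be meant as the period-1 size, that is 1/k. Table 5 is said to come from these steps and lies closer to the 1/k form, which suggests that the sponsor's simulations were coded correctly. This may well be so, but the printed definition of k_1 says otherwise and the documents do not show the program. The Table 5 comparison is also only suggestive: the simulation has no covariates, an approximate posterior, an assumed follow-up profile (information 0.64 against the SAP's 0.60) and two identical studies, whereas Table 5 shows different power for each.

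The effect at the design rate ratio is small, and the larger shifts lie near 0.7, where the SAP already expects futility to trigger. That stands. So does the point that the IDMC sees other outputs and must agree before a decision is passed on.

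The SAP amendments of December 2023 and April 2024 may mean that the interim had already passed without a stop. The documents do not say so. If it had, and k was below 1, a decision to continue under the printed form would usually be the same under the 1/k form. That limits the harm but does not make the printed rule right.

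**Conclusion.** The concern holds. Step 3.3 as printed contradicts its own probability line and the model in step 2. Taken literally at k near 0.8, it under-predicts post-interim exacerbations by about a quarter to a third and adds roughly 5 to 9 points to the futility probability at true rate ratios of 0.6 to 0.7, but only about 1 point at 0.5. These sizes rest on k near the planning value, on literal coding and on a simplified simulation; the sign reverses above k = 1. Whether the error reached the program cannot be judged from the documents. Final inference and type I error are not affected. It should be fixed because the SAP, followed as written, gives a wrong predictive probability for a decision that can stop both pivotal studies.

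**What to change.** In step 3.3, print the size as 1/k + count, with the same sampled k as in the p line; or define k_1 as 1/k and stop calling it the dispersion. Confirm that the SDAC program and the IDMC charter use this form. If the interim was run with the printed form, recompute the predictive probability and record the result for the IDMC. The cost is a one-line correction to the SAP (and to the charter if the line is repeated there) plus a code check. It needs no additional participants and does not alter study conduct.
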